### 4.7.8 Multiple comparison adjustments

The methods of signal surveillance require a large number of multiple comparisons on adverse events, which involve inferring statistical significance on multiple *p*-values. To control for an excess of false positive signals, suitable multiple comparison adjustments will be made with the false discovery rate (FDR) approach. [41] The Simes method [42;43] in addition to the double FDR method [41] will be implemented to maintain the false discovery rate at the acceptable 10% level for all statistical tests. Such approaches would allow for a balance between false positive and false negative signals.

# 4.8 Aggregate Assessment of Drug- Relatedness of Selected Events

As described previously (section 4.4.1.3) selected events of interest (Table 4) that require further characterisation and evaluation may be followed-up via a questionnaire sent to the responsible specialist HCP or patient's GP seeking further information. The information received at follow-up for events of medical significance or those which require further clarification will facilitate further evaluation at the aggregate level , including collective assessment of drug-relatedness, by experienced research staff at the DSRU (two qualified members of staff, independently, with a third adjudicator if necessary). The aim of the collective drug-relatedness assessment for groups of events during the analysis of the interim and final reports, is to put events in context regarding temporality co-morbidity, pre-existing disease and concomitant medications. This aggregate assessment of event data occurs at interim or final report for cases for which all requested information (i.e. index date questionnaire, 12 week end of observation questionnaire, and follow-up questionnaire if applicable) has been received. In the process of aggregate assessment of event data, the application of elements of the Austin Bradford Hill criteria, when the necessary information is available and the use of the method is considered appropriate, will be used (see Box 1).[44]

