- Medical history relevant for important potential, identified and special risks of interest (plus dates of first diagnosis/report). For example: past history of DVT/PE, myocardial infarction (MI), percutaneous coronary intervention (PCI), coronary artery bypass graft (CABG), other recent surgery within 3 months prior to index date, malignancy, pregnancy, family and/or personal history of congestive heart failure, diabetes mellitus, hypercholesterolaemia, peripheral arterial disease, COPD etc.)
- Specific information on renal function status at index date and any changes during 12 week observation period
- Specific information on hepatic disorders present at index date (cholestasis and jaundice, hepatic failure and associated disorders, hepatic fibrosis and cirrhosis and hepatic viral infections) and any recent abnormal liver function tests.

Version 40 20/11/2014 REC Ref 12/SC/0592

##### for rivaroxaban only

- event reports including selected risks of interest (Table 4)
- o cause and date of death (if died) in the first 12 weeks after starting treatment;
- reported pregnancies at start or during the first 12 weeks after starting treatment and outcome of birth.
- behaviours prior to and/or starting treatment (e.g. smoking, alcohol/substance misuse); treatment adherence

Risk/Missing Information	Proposed data capture	Comment
IDENTIFIED, POTENTIAL AND SPECIAL RISKS A	ND OUTCOMES for targeted data	collection on SCEM questionnaires
Major bleeding episode (into a critical organ	Targeted outcome questions on	Selected risk factors collected on SCEM
sites )	critical sites	questionnaire. Further data on severity,
		management and risk factors to be collected
		via follow-up.
Clinically relevant minor bleeding episodes	Targeted outcome question to	Selected risk factors collected on SCEM
	specify details	questionnaire. Not for follow-up
Incident and recurrent thromboembolic	Targeted outcome questions	Selected risk factors collected on SCEM
complications (DVT, PE, Stroke)		questionnaire. Further data on symptoms,
		severity, management and risk factors to be
		collected via follow-up.
Overdose. accidental trauma and Reversal of	Targeted outcome question	Events of overdose (dose > 50mg/day) and
anticoagulation therapy		accidental trauma are those of clinical
		medical importance which require acute
		medical/surgical treatment (with or without)
		hospitalisation Further data to be collected
	-	via follow-up

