# 4.4.2.5 Follow-up Questionnaires

During the course of the study, selected outcomes of interest (arising from Section 2.2) may undergo further evaluation for aggregate assessment of drug- relatedness to inform on any unusual features/manifestations, relevant risk factors, clinical course and behaviours (see section 4.8). Where necessary, a supplementary follow-up questionnaire which is bespoke to the outcome of interest may gather additional relevant information where recorded within medical charts. [37]

With the exception of these enquiries for additional information on selected events, no further monitoring of patients for purposes of data collection will occur post the survey period. In accordance with Good Pharmacovigilance Practice (GVP) sections VI.C.1.2.1 and VI.C.2.2.2, [38] data will be analysed at aggregate level partially at the time of compiling the interim report (because all information may be available then) and at study completion. Such aggregate analyses can help formulate possible hypotheses which then require further analytic study. Because of the epidemiological nature of the design of this cohort study, any *conclusions* on drug-relatedness will be made on aggregate basis at study milestones, i.e. when the interim and final reports are written (see Section 4.9.2 on Communications).

If any other safety issues become apparent during the conduct of this study, additional events and/or event categories may be added to the list of events for follow up and this will be documented accordingly.

Specific events of interest for further evaluation:

1. Pregnancies: All reported pregnancies will be followed-up using a supplementary questionnaire to describe the outcome of pregnancy§§§§§.

<sup>§§§§§§ Drug-relatedness assessments of abnormal birth outcomes are not conducted by the DSRU

- 2. Deaths: All reported deaths will be followed-up to try to establish the cause of death.
- 3. Events: Selected events of interest as defined in Table 4 may be followed-up for additional information on relevant risk factors, where insufficient information is provided on the questionnaire. The event of switching given as a reason for stopping rivaroxaban (although not defined in Table 4) will undergo further evaluation.

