- 4. Adverse events: Other adverse events deemed of medical importance by the DSRU which are considered to be possible safety signals (either arising from literature reports post marketing, or subsequent to interim data analysis) may also be followed-up for additional information on relevant risk factors for signal strengthening purposes.
- 5. Adverse events: Events within the list of Rare and Iatrogenic Adverse Reactions (RAIDAR) compiled by the DSRU (Appendix 2) will be automatically followed up if a more likely alternative explanation for their occurrence is not given.

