# Box 1. Points for consideration in collective evaluation of reported events

- The distribution of time to onset (temporal relationship);
- The principle clinical and pathological characteristics of the group of events;
- The pharmacological plausibility based on previous knowledge of the drug and the therapeutic class if appropriate;
- Similar reports in medical literature
- patient's clinical characteristics, including:
- previous medical history, such as history of drug allergies, presence of renal or hepatic impairment, etc.

-concomitant medications or medications taken prior to and during treatment;

• Management and remedial action;

The collective drug-relatedness of selected groups of events of interest will be categorised in terms of proportions of reports assessed within the following four categories: 1) probable\*\*\*\*\*\*\*, 2) possible†††††††, 3) unlikely‡‡‡‡‡‡‡‡, and 4) not assessable§§§§§§§. [45]

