# 4.9 Data Monitoring

# 4.9.1 Project Steering Committee

A Project Steering Committee (PSC) will be set up to be comprised of the study investigators and other experts. The role of the PSC will be to oversee the smooth running of the project and provide scientific, statistical and technical advice when needed and will meet at regular intervals (3 to 12 monthly depending on the stage of the study, either in person or by teleconference).

\*\*\*\*\*\*\* Events are assessed as 'probable' if the event is well defined clinically and pathologically, if there is a reasonable time sequence, if it is more likely to be attributed to the study drug rather than to a concurrent disease or concomitant medication, if there is a positive dechallenge, rechallenge or response to dose increase, and if there are other supporting criteria (e.g. on the basis of lab tests or histological findings).

tititit Events are assessed as 'possible' if the event has a reasonable clinical and pathological definition, if there is a reasonable time sequence, if it could also be explained by concurrent disease or concomitant medication, but dechallenge, rechallenge and confirmatory investigations are inconclusive or not fully available. Medical judgement will be necessary in some cases.

<sup>+++++++ Events are assessed as unlikely if the event had a temporal relationship to the study drug administration that made a causal relationship improbable, or if concurrent disease or concomitant medication provided a far more plausible explanation. §§§§§§§ Events are unassessable if insufficient information about the event has been provided and an appropriate evaluation is therefore not possible.

The PSC is broadly analogous to a Safety Monitoring Committee or Review Board, but the purpose may be slightly different such that the PSC includes investigators and also oversees the effective progress of the study. The first PSC meeting will orientate the project team members and establish the logistics for specialist and patient recruitment and confirm patient inclusion criteria. Subsequent PSC meetings will clarify the understanding of the ongoing project requirements, monitor progress through assessment of data within the interim reports [specialist/cohort accrual rates, preliminary analyses of individual variable responses on questionnaires], consider any additional proposed inclusion criteria, and act as a forum to review and discuss any queries.

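### Section 4.8 assesses drug-relatedness only for cases with every requested form received, so, as written, an event whose follow-up form never returns drops out of the reported proportions

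*Supplement*

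**What the plan says.** Three parts of the protocol bear on this.

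- **Who is assessed.** Section 4.8: "This aggregate assessment of event data occurs at interim or final report for cases for which all requested information" has been received. It names the index date form, the 12-week form and the follow-up form if one applies.
- **What is reported.** Under Box 1 in 4.8, drug-relatedness of a group of events is expressed "in terms of proportions of reports assessed within the following four categories": probable, possible, unlikely and not assessable. The footnote to the last category reads "Events are unassessable if insufficient information about the event has been provided" and appropriate evaluation is therefore impossible.
- **What it is for.** Section 4.4.2.5 says conclusions "on drug-relatedness will be made on aggregate basis at study milestones, i.e. when the interim and final reports are written".

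Several rules decide which events get a follow-up form. Table 4 sets it by event type: further data on major bleeds are to be collected through follow-up, while clinically relevant minor bleeds are marked "questionnaire. Not for follow-up". Section 4.4.2.5 adds deaths ("All reported deaths will be followed-up to try to establish the cause of death"), events on the list of rare and iatrogenic reactions (they "will be automatically followed up if a more likely alternative explanation for their occurrence is not given"), and Table 4 events that may be "followed-up for additional information on relevant risk factors, where insufficient information is provided on the questionnaire".

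Section 4.4.3.2 provides a duplicate form for non-responders and payment for each completed form. No section says what happens to an event if the form still does not arrive.

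**The concern.** This is a complete-case rule on a safety summary. An event enters the assessment because paperwork was returned, not because of anything known about the event. The plan already has a category for events with too little information, yet the entry rule keeps out the events most likely to belong there, leaving that category to forms that came back uninformative.

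The loss need not be random. Follow-up is requested partly by event type and partly because detail is missing, so the events exposed to the rule differ from those that are not. An event on the rare-reactions list is automatically followed up only if no likelier explanation was offered, so within that list the unexplained events are the ones that can be lost this way. Across all selected events the direction of bias cannot be stated.

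At stake are the proportions that support the study's aggregate conclusions on causality.

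**Working it through.** **1. Does the text exclude these events?** Section 4.8 makes receipt of all applicable forms the condition for assessment at either report. Box 1 reports proportions of the reports assessed. An event with an outstanding follow-up form fails the condition, is not assessed, and is in neither numerator nor denominator. The denominator is implied by this wording; it is not defined anywhere.

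**2. Does another section rescue them?**
- The *not assessable* footnote refers to insufficient information, not to a form that was never returned.
- Section 4.5.2 leaves missing-data methods to a Data Management Plan and the steering committee in general terms. It does not amend the rule in 4.8.
- The planned look at excluded incomplete cases in 4.7.2 concerns the incidence of major bleeding, not relatedness.

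**3. How far can a share move?** The plan gives no figure to reproduce here. Let N be the selected events in a group, u those dropped, and a the number in a given category among the N − u assessed.
- Reported share: p = a/(N − u).
- All-event share: between a/N and (a + u)/N.
- p − a/N = p·u/N, and (a + u)/N − p = (1 − p)·u/N.
- Both gaps are at most u/N.

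**4. A plausible N from the plan.** Section 4.2.1 assumes 12-week primary-site bleed incidence of 0.4% (DVT/PE) and 0.7% (AF), with minimum numbers of 1005 and 561.
- At the minima: 1005 × 0.004 + 561 × 0.007 = 4.02 + 3.93 = 7.95.
- At 1700 split 2:1 in favour of DVT/PE: 1133.3 × 0.004 + 566.7 × 0.007 = 4.53 + 3.97 = 8.50.

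So there are about 8 events, pooling three sites and both indications.

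**5. The bound.**

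| N | u | Largest possible shift (u/N) |
|---|---|---|
| 8 | 1 | 12.5 points |
| 8 | 2 | 25 points |
| 50 (assumed) | 2 | 4 points |

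The bound is reached only when all or none of the assessed events fall in the category. A middling case with N = 8, u = 1, a = 4: the reported share is 4/7 = 57.1%, and the all-event share is 4/8 = 50.0% or 5/8 = 62.5%.

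**6. Range over an assumed non-return rate m.** Suppose 50% of complete cases are *probable*. The rule reports 50% whatever m is.

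| m (assumed) | *Probable* if all unreturned are *not assessable* | Limits |
|---|---|---|
| 10% | 45% | 45–55% |
| 20% | 40% | 40–60% |
| 30% | 35% | 35–65% |
| 40% | 30% | 30–70% |

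**The case against.** The strongest reply is that the sentence sets timing, not eligibility: a case goes to whichever report follows completion of its file. Section 4.4.2.5 does describe the interim analysis as partial. The existence of *not assessable*, and a definition of *possible* that tolerates incomplete investigations, suggest the authors meant to keep poorly documented events. Detail on denominators could also sit in the Data Management Plan or an SAP, neither of which is shown. Non-return is already mitigated by duplicate forms and payment.

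The timing reading works at the interim, where an incomplete case can wait. It fails at the final report, because the same condition applies there and no later report follows. If the authors intended such events to be *not assessable*, 4.8 says otherwise and needs the same correction. A denominator could properly be left to an SAP, but 4.8 does not leave the point open; it states an entry rule. Reminders reduce the number lost but do not say how the remainder are handled.

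What stands is the argument about weight. The proportions feed a collective, qualitative judgement with no threshold attached, and section 4.4.2.5 describes these analyses as forming hypotheses. The u/N bound is an identity; it says what is possible, not what is likely.

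**Conclusion.** The concern holds on the text as written. An event with a never-returned follow-up form falls outside the relatedness proportions at the final report. The *not assessable* share may be too low, and the other shares may be off in either direction.

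The size is unknown because no return rate is given. The shift is limited to u/N: at most 12.5 points for each missing form in a group of 8, and smaller in larger groups. The figure of 8 assumes that the incidences in section 4.2.1 apply and that the recruitment targets are met.

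The effect is confined to this descriptive summary. Primary bleeds are adjudicated under 4.7.2 on all the information available, and event risks and rates do not use the complete-form rule. This should be corrected, but it does not threaten the primary objective. Confidence is moderate, because the authors may have intended something other than what 4.8 says.

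**What to change.** Replace the entry condition in 4.8 with one or two sentences to this effect:

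- At the final report, every selected event is assessed on the information held. It is classed *not assessable* only if that information is insufficient.
- The denominator is all selected reported events in the group, and the number with follow-up unreturned is shown beside each proportion.
- At the interim report, cases with forms outstanding are listed as pending.

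This uses the existing forms, the same assessors and the plan's own four categories. The cost is a visibly larger *not assessable* share.

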# Box 1. Points for consideration in collective evaluation of reported events

- The distribution of time to onset (temporal relationship);
- The principle clinical and pathological characteristics of the group of events;
- The pharmacological plausibility based on previous knowledge of the drug and the therapeutic class if appropriate;
- Similar reports in medical literature
- patient's clinical characteristics, including:
- previous medical history, such as history of drug allergies, presence of renal or hepatic impairment, etc.

-concomitant medications or medications taken prior to and during treatment;

• Management and remedial action;

The collective drug-relatedness of selected groups of events of interest will be categorised in terms of proportions of reports assessed within the following four categories: 1) probable\*\*\*\*\*\*\*, 2) possible†††††††, 3) unlikely‡‡‡‡‡‡‡‡, and 4) not assessable§§§§§§§. [45]

# 4.9 Data Monitoring

# 4.9.1 Project Steering Committee

A Project Steering Committee (PSC) will be set up to be comprised of the study investigators and other experts. The role of the PSC will be to oversee the smooth running of the project and provide scientific, statistical and technical advice when needed and will meet at regular intervals (3 to 12 monthly depending on the stage of the study, either in person or by teleconference).

\*\*\*\*\*\*\* Events are assessed as 'probable' if the event is well defined clinically and pathologically, if there is a reasonable time sequence, if it is more likely to be attributed to the study drug rather than to a concurrent disease or concomitant medication, if there is a positive dechallenge, rechallenge or response to dose increase, and if there are other supporting criteria (e.g. on the basis of lab tests or histological findings).

tititit Events are assessed as 'possible' if the event has a reasonable clinical and pathological definition, if there is a reasonable time sequence, if it could also be explained by concurrent disease or concomitant medication, but dechallenge, rechallenge and confirmatory investigations are inconclusive or not fully available. Medical judgement will be necessary in some cases.

<sup>+++++++ Events are assessed as unlikely if the event had a temporal relationship to the study drug administration that made a causal relationship improbable, or if concurrent disease or concomitant medication provided a far more plausible explanation. §§§§§§§ Events are unassessable if insufficient information about the event has been provided and an appropriate evaluation is therefore not possible.

The PSC is broadly analogous to a Safety Monitoring Committee or Review Board, but the purpose may be slightly different such that the PSC includes investigators and also oversees the effective progress of the study. The first PSC meeting will orientate the project team members and establish the logistics for specialist and patient recruitment and confirm patient inclusion criteria. Subsequent PSC meetings will clarify the understanding of the ongoing project requirements, monitor progress through assessment of data within the interim reports [specialist/cohort accrual rates, preliminary analyses of individual variable responses on questionnaires], consider any additional proposed inclusion criteria, and act as a forum to review and discuss any queries.

### 4.9.2 Communications

Progress reports (relevant to specialist and patient cohort accrual) will be produced in time for inclusion in the scheduled Periodic Safety Update Reports for the product (i.e., every six months for the first two years after launch and then annually thereafter) or regular updates of the RMP for as long as the study continues. Examination of aggregate event data will be limited to one interim report based on the evaluable study cohort achieved at approximately 18 months post date of first patient recruited, and a detailed final report based on the evaluable study cohort achieved at approximately 36 months post date of first patient recruited. It is anticipated that the final cohort for analysis will be comprised of 3400 evaluable patients with relevant indications. However the final sample size achieved within this timeframe will be governed by application of NICE guidance (which can vary) between secondary care trusts and managed entry, therefore the possibility of a requirement to extend the study period must be acknowledged.

### 4.9.3 Adverse event /reaction reporting

This registry-based, observational, non-interventional cohort study is based on secondary use of data, therefore adverse reactions reporting is not required. Reports of adverse events/reactions will be summarised in the study report, where applicable. The DSRU shall, on an ongoing basis, notify the MAH when they consider, based on their evaluation, that any issues or matters of interest relating to the Study or its outcomes are of importance and shall provide the MAH with related results of the study and analyses thereof.

Since the clinicians are prescribing a licensed product, they will be reminded in the study documentation that it is their responsibility to report any suspected adverse reactions (including serious\*\*\*\*\*\*\*\* adverse drug reactions) to the company and/or to the MHRA (using Yellow Cards) as they would normally do in their practice in support of routine pharmacovigilance. In cases where the DSRU receives, by mistake, such reports it will forward them to the MHRA and/or the MAH as appropriate.

